After an overnight fast (> 10 hours), study subjects will report to LSU Exercise Physiology Laboratory to complete V4. V4 will be scheduled 48 hours after the subject's last training session. During this visit, we will measure height, weight and vital signs. During this visit, we will ask subjects to complete the International Physical Activity Questionnaire-Elderly,¹⁹ Sedentary Behavior Questionnaire,²⁰ and PROMIS Physical Function Questionnaire^{21, 22}, and the Pittsburgh Fatigability Questionnaire. We will also measure the body composition by DXA and BIA. We will also perform the MMTT as described for V1. We will also draw fasting and MMTT associated bloods as described for V2 (total blood volume of about 150 ml or 10-12 tablespoons total). The analyses performed on these blood samples collected in V4 will be as described for V2.

Posttraining V5 (About 3.5-4 hours)

After an overnight fast (> 10 hours), study subjects will report to PBRC to complete V5. V5 will be scheduled about 72 hours after the subject's last training session. During this visit, we will measure height, weight and vital signs. We will measure body composition using standard circumferences, optical imaging, and BIA, which will be conducted in [name] Laboratory. During this visit, we will collect a fasting blood sample (~ 10 ml). We will also perform the MRI for leg muscle mass, Phosphorous Magnetic Resonance Spectroscopy – ³¹P-MRS, and Muscle Biopsy as described for V3. During V5, subjects who agree to the optional Carbon-13 magnetic resonance spectroscopy procedure will do that procedure.

STUDY ENDPOINTS

Primary Endpoints

1. Comparison of within and between group changes in muscle strength, mass, and quality (strength/mass) using isokinetic dynamometry and DXA (primary outcomes Aim 1) between treatment groups.
2. Comparison of within and between group changes in body composition by DXA, fasting blood glucose and lipids by a clinical chemistry panel and glucose tolerance by a mixed meal tolerance test (primary outcomes Aim 2)

Safety Endpoints

1. Safety will be monitored by adverse event reporting (See Data Safety Monitoring Plan).

DETAILED METHODS AND ANALYSIS

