[name] (LSU) and [name] (PBRC). We will screen all data for distributional properties (mean, median, range) and departures from normality prior to substantive analyses. To test the main effects of time, treatment, and their interaction on the primary outcomes, we will use mixed-effects two-way Analysis of Variance (ANOVA) models ($\alpha=0.05$). The models will include parameters to estimate the main effects of time (pre- and post-training) and treatment (RE, REALPA breaks in ST, RE+AE) on the dependent variables. We will use *Fisher's Least Significant Differences test* to examine within and between group mean differences ($\alpha=0.05$). We will test all models for the main effect of sex. If the main effect of sex is significant, we will perform additional exploratory analyses stratified by sex. Other covariates that may be included in the models include race, change in body weight, and baseline SPPB scores. We will also compare adherence rates across the study groups.

Sample Size, Power Analysis and Randomization. We will use the data collected in this **pilot study** to estimate effect sizes for the primary and secondary outcomes, which we will use to inform our power analyses for a follow-up R01 application designed to test the efficacy of our novel exercise intervention on skeletal muscle and cardiometabolic health in sedentary older adults. We will use a fixed sample size of 12 subjects per group, because increasing the sample size above 12 (i.e., 12 to 15) has diminishing benefit in estimations effect sizes and 95% confidence intervals often referred to as the “rule of 12”.^{39, 40} Thus, we will recruit up to 15 subjects per group to account for a 20% attrition rate. The NIH’s Clinical and Translational Science Awards Biostatistics, Epidemiology, and Research Design (BERD) units recommend 12 subjects per group for estimating effect sizes and 95% confidence intervals.³⁹ Following baseline testing, we will randomize the study subjects to one of the three interventions using a randomized, permuted, block design stratified by sex and race.

PROVISIONS TO MONITOR THE DATA TO ENSURE THE SAFETY OF SUBJECTS

This Human Subjects Research meets the definition of a Clinical Trial. This study does not involve major risk to subjects. Efforts to minimize the potential risks of the assessment methods and outcome variables include frequent monitoring by the investigators to assure that no volunteer suffers any adverse effects from participating in the research.

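### The primary endpoints are changes, but the plan also tests a treatment main effect averaged over pre- and post-training values and does not say which test decides the between-group question

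*Combined protocol and SAP*

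**What the plan says.** Under Study Endpoints, both primary endpoints of the combined protocol and SAP are changes: "Comparison of within and between group changes in muscle strength, mass, and quality" for Aim 1 and "Comparison of within and between group changes in body composition by DXA, fasting blood glucose and lipids" for Aim 2.

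The section Data Management and Primary Statistical Analyses plans a mixed-effects two-way ANOVA at alpha 0.05. Its purpose is given as "To test the main effects of time, treatment, and their interaction on the primary outcomes". The following sentence reads "The models will include parameters to estimate the main effects of time (pre- and post-training) and treatment" and does not repeat the interaction. Fisher's LSD, also at 0.05, is then used "to examine within and between group mean differences". The text does not say whether the between-group differences are in change, in post-training means, or in means averaged over both times. Sex is tested as a main effect. Race, weight change and baseline SPPB are optional covariates, and the baseline value of the outcome is not listed.

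The section Sample Size, Power Analysis and Randomization states "Following baseline testing, we will randomize the study subjects to one of the three interventions". It fixes 12 completers per group and says that effect sizes from this pilot will inform the power analysis of the follow-up application.

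**The concern.** With two time points, the treatment main effect compares arms on the average of each person's pre- and post-training values. Half of that average was measured before allocation and cannot carry a treatment effect. The test therefore does not address the endpoint, which is a difference in change, yet the plan gives it the same standing and the same alpha as the test that does.

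Three things could follow. A significant treatment effect could be reported when the arms mainly started out different. A real between-arm difference could be read as no effect of treatment although the interaction shows it. And if the undefined LSD differences were taken as means averaged over time, the effect size carried to the follow-up application would be halved in raw units. With the SD held fixed, required sample size varies with the inverse square of the difference, so halving the difference would multiply it by 1/0.5² = 4.

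**Working it through.** **The plan's own figure.** 12 completers per group with 20% attrition gives 12/0.8 = 15 per group, and 36/0.8 = 45 in total. Both match the document. The 12 is a cited rule of thumb. No power, effect size, SD or pre-post correlation is stated, so there is no power figure to reproduce.

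**Inputs.** From the document: n = 12 per arm, three arms, alpha 0.05, randomization after baseline testing. Assumed: two-sided tests, equal SD s at both times, pre-post correlation rho from 0.5 to 0.9, and a true difference in change between two arms of d = 1 SD.

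**What each contrast estimates, for two arms.**
- Treatment main effect, on (pre + post)/2: expectation (0 + d)/2 = d/2; variance per subject s²(1 + rho)/2.
- Time-by-treatment, on post − pre: expectation d; variance per subject 2s²(1 − rho).
- Post-training value adjusted for baseline: expectation d; variance per subject s²(1 − rho²).

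The SE of each contrast is sqrt(2 × variance/12). The halving is algebra and does not depend on s, rho or n.

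**Numbers at rho = 0.8, d = 1 SD.**
- Main effect: SE = sqrt(2 × 0.90/12) = 0.387; 0.5/0.387 = 1.29.
- Interaction: SE = sqrt(2 × 0.40/12) = 0.258; 1/0.258 = 3.87.
- Baseline-adjusted: SE = sqrt(2 × 0.36/12) = 0.245; 1/0.245 = 4.08.

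Power from the noncentral t with 33 df (the adjusted analysis would strictly lose one more):

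| rho | Main effect | Interaction | Baseline-adjusted post value |
|---|---|---|---|
| 0.5 | 28% | 66% | 78% |
| 0.7 | 25% | 87% | 91% |
| 0.8 | 24% | 96% | 98% |
| 0.9 | 23% | over 99% | over 99% |

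At d = 0.5 SD the ranges are 9–11%, 22–76% and 28–78%.

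**Check by simulation** (20,000 trials, rho 0.8, a gain of 0.5 SD shared by all arms plus 1 SD more in two of them). The main-effect contrast averaged 0.50 SD and the interaction contrast 1.00 SD. A mixed model fitted to constructed data gave 0.500 for the treatment coefficient without the interaction term, and 1.000 for the interaction coefficient when it was included.

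**Chance baseline imbalance.** The SE of a baseline difference between two arms is sqrt(2/12) = 0.41 SD. In the simulation, the main-effect estimate moved by 0.90 SD per 1 SD of baseline difference, and the interaction estimate by −0.21.

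**Under the null.** With equal variances, the sum and the difference of pre and post are uncorrelated. The two tests are then nearly independent, and the chance that at least one is significant is about 1 − 0.95² = 0.0975; simulation of the three-arm F tests agrees, at about 10%. Each test alone holds its 5%. At rho 0.8, about two thirds of the significant main effects came with a baseline difference significant at 0.05.

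**The case against.** The strongest reply is that the interaction stands in the same sentence as the main effects, is tested at the same alpha, and is exactly the between-group difference in change. That is correct. A reader might infer that the plan delivers only half of any training effect, and the document does not support this. The interaction recovers the full between-group difference. A gain shared by all arms, which the protocol expects because every arm does the same resistance training, cancels from the treatment term and shows in the time effect. For the same reason, 24% against 96% power at rho 0.8 is not a loss under the plan, because both tests are in it.

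A reader might also infer an inflated false-positive rate for the main-effect test. There is none: after randomization, chance imbalance is already in its standard error. The weakness is in what a significant result means, and in having two tests with no rule for when they disagree.

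The LSD wording can fairly be read as contrasts of change, since the endpoints pair within- and between-group comparisons in the same way and a within-group mean difference is a change. Nor does any section say that effect sizes for the follow-up application will come from the treatment main effect. Both points stand. They show that a sound reading is available, not that the text requires it, and the sentence listing only main-effect parameters points the other way.

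**Conclusion.** The point holds as a mismatch between a stated test and the stated endpoint. The treatment main effect estimates half of any between-group difference in training effect and carries chance baseline imbalance, yet it has equal standing with the interaction, which estimates the endpoint itself. The halving needs only randomization after baseline and two time points. The power figures (28% to 23%, against 66% to over 99%) rest on the assumed 1 SD difference and correlations of 0.5 to 0.9, and show how often the two tests could disagree. The roughly 10% chance of at least one significant result under the null assumes equal variances at the two times. The plan as a whole still contains the right test, so what needs correcting is which result is decisive and how the others are read. It should be settled before analysis.

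**What to change.** In Data Management and Primary Statistical Analyses:

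1. Keep the treatment term in the model, but do not test or interpret it as evidence of a between-group effect.
2. List the time-by-treatment interaction among the model parameters.
3. Name one decisive between-group estimate, with its 95% CI: either the difference in change (time by treatment) or the post-training value adjusted for the baseline value of the outcome. Under the assumptions above, the adjusted analysis is somewhat more powerful at the lower correlations (78% against 66% at rho 0.5).
4. State that the between-group LSD comparisons, and the effect sizes carried to the follow-up application, use that estimate, and not means averaged over time or unadjusted post-training means.

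The cost is wording only. One uninformative p-value per outcome is lost, and no data collection or sample size changes.

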Although awareness of the detrimental impact that sedentary behavior has on skeletal muscle and cardiometabolic health has increased over the last 20 years, more than 60% of older adults remain sedentary for greater than 8 hours per day. Moreover, 80% to 90% of adults 60 years of age or older do not meet the current public health guidelines for aerobic exercise (AE) or resistance exercise (RE) based physical activity (PA). Collectively, these adverse health behaviors contribute to the development of multiple chronic medical conditions commonly afflicting older adults, including type 2 diabetes, cardiovascular disease, sarco/dynapenia, frailty, and premature mortality. Emerging evidence suggests that breaking up sedentary time with light intensity PA (LPA) improves muscle and cardiometabolic health. Recent data also suggest that RE combined with moderate intensity AE effectively improves muscle and cardiometabolic health in older adults. However, the impact that RE combined with LPA breaks in sedentary time has on muscle and cardiometabolic health in older adults remains unknown. The overall objective of this pilot study is to determine the effect of 16 weeks of RE alone or RE combined with LPA breaks in sedentary time on muscle and cardiometabolic health. The central hypothesis is that the addition of LPA breaks in sedentary time will enhance RE-induced improvements in muscle and cardiometabolic health in sedentary older adults. Our overall approach to test our central hypothesis is to recruit and study 36 physically inactive community dwelling older adults (65-80 years) who are randomized to 16 weeks of either (i) RE (2 x/wk), (ii) RE (2 x/wk) and LPA breaks in sedentary time (5 d/wk, 6x10 min breaks per day at 2 METS, ~500 kcal/wk above resting metabolism), or (iii) RE (2 x/wk) and moderate intensity AE (3 d/wk, 50 min/session at 4 METS, ~500 kcal/wk above resting metabolism). The effect that these PA interventions have on muscle health will be measured by changes in muscle strength, mass, and quality (strength/mass) using isokinetic dynamometry and dual-x-ray absorptiometry (DXA) (primary outcomes). In addition, improvements in muscle oxidative capacity will be measured using high-resolution respirometry and oxidative damage to muscle proteins by immunoblotting (secondary outcomes). The effect

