that these PA interventions have on cardiometabolic health will be measured by changes in body composition by DXA, fasting blood glucose and lipids by a clinical chemistry panel and glucose tolerance by a mixed meal tolerance test (primary outcomes). Additionally, improvements in immunometabolic health will be measured by changes in low-grade systemic inflammation (e.g., TNF α) using immunoassays and immune cell oxidative capacity by high-resolution respirometry (secondary outcomes). The proposed studies will provide preliminary evidence that LPA breaks in sedentary time enhance RE- induced improvements in muscle and cardiometabolic health in older adults, will further evaluate efficacy in a follow-up R01 randomized clinical trial.

OBJECTIVES

The *overall objective* of this pilot study is to determine the effect of 16 weeks of resistance exercise (RE) alone or RE combined with low intensity physical activity (LPA) breaks in sedentary time (ST) on muscle and cardiometabolic health in older adults.

HYPOTHESIS AND SPECIFIC AIMS

We *hypothesize* that the addition of LPA breaks in ST will enhance RE-induced improvements in muscle and cardiometabolic health in sedentary older adults.

Specific Aim 1. To evaluate the effect of resistance exercise (RE) alone or with regular low intensity physical activity (LPA) breaks in sedentary time (ST) on skeletal muscle health in older adults. Our *working hypothesis* is that regular LPA breaks in ST will enhance RE-induced improvements in muscle health in older adults. *Outcomes:* We will measure muscle strength, mass, and quality (strength/mass) using isokinetic dynamometry and dual-x-ray absorptiometry (primary outcomes). We will measure muscle OXPHOS using high-resolution respirometry and oxidative damage to muscle proteins by immunoblotting (secondary outcomes).

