Exercise Interventions. After completing V2, we will randomize the subjects to one of three 16-week interventions: (i) RE, (ii) REALPA breaks in ST, or (iii) RE+AE (**Figure 3**). The RE+AE group serves as the standard of care. The RE group will complete supervised RE (2 x/wk). The REALPA breaks in ST group will complete a supervised RE (2 x/wk) and regular unsupervised LPA breaks in ST (5 d/wk, 6x10 min breaks/d at 2 METS (~30-40% VO_2 peak), ~500 kcal/wk above resting metabolism). The RE+AE group will complete supervised RE (2 x/wk) and calorically matched moderate intensity AE (3 d/wk, 50 min/session at 4 METS (~60-75% VO_2 peak), ~500 kcal/week above resting metabolism). The RE component for all 3 groups will consist of 3 sets of 10-12 repetitions to failure for a total of 8 exercises targeting the large muscle groups (**Table 2**). The AE component for the RE+AE group will consist of treadmill walking at ~4 METs for 50 min

(Table 2). The RE and AE sessions will take place in LSU School of Kinesiology's Exercise Training Facility under direct supervision (Drs. [name], [name], and [name] with the assistance of trained graduate students). All supervised exercise sessions will include a 5 minute warm-up and cool-down on either a bike or treadmill. We will provide subjects flexibility on the days per week that they can complete their exercise sessions. Note: The start of the exercise intervention will be at least 5 days post V2 to allow for adequate recovery from the muscle biopsy, but no more than 6 weeks after V2. Up to 2 weeks may be added to a subjects exercise intervention, to allow for potential make-up of missed exercise sessions and to provide flexibility for scheduling study visits.

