Table 2. The RE group will complete supervised RE (2x/wk) (A). The REALPA breaks in ST group will complete supervised RE (2x/wk) and regular unsupervised LPA breaks in ST (5x/wk) (A+B). The RE+AE group will complete supervised RE (2x/wk) and calorically matched moderate intensity AE (3x/wk) (A+C).

Physical Activity Monitoring During Intervention. To quantify total physical activity throughout the intervention, we will ask that subjects wear a physical activity monitor (Actigraph, GT9X) on their wrist 24 h/d for the duration of the study and a second physical activity monitor (Actigraph, GT9X) on their thigh during weeks 1, 4, 8, 12, and 16 for further quantification. We will screen raw data from these monitors for periods of valid wear-time with a required minimum wear-time of 10 h per valid wear-day and 4 valid wear-days per week.^{23,24} We will use standard algorithms to characterize the patterns of PA and ST.²⁵

Adherence Monitoring During Intervention. We will monitor each subject's attendance to the prescribed exercise training sessions and exercise training logs to assess adherence to the exercise intervention. We will also use the physical activity monitoring data to help assess adherence to the exercise intervention. De-identified physical activity monitoring data will be uploaded to the CentrePoint Cloud-Based Data Capture and Management Platform to facilitate data collection and monitoring.

Visit 3 (V3) (End of Exercise Intervention). During last week of the intervention (i.e., week 16), subjects will be asked to complete V3, with two parts. Part I will occur PBRC and Part II at the LSU Exercise Physiology Laboratory on the main campus of LSU.

V3, Part I (about 2 hours).

After an overnight fast (> 10 hours), subjects will report to PBRC to complete V3, Part I. During this visit, we will measure height, weight and vital signs. We will then perform the SPPB and Exercise Test (VO₂ Peak).

V3, Part II (about 1 hour).

Subjects will report to LSU Exercise Physiology Laboratory to complete V3, Part II (non-fasted). The visit procedures for this visit can be done at a regularly scheduled exercise session and would be completed prior to the start of that day's exercise. During this visit, we will conduct the Biodex, 1-RM, and Handgrip Strength and Endurance Testing.

Posttraining Visit 4 (V4) (About 5 hours).

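### Change in body weight, a post-randomisation variable, may enter the primary models with no form of entry or inclusion rule, and can distort the REALPA-versus-RE effects on fat and lean mass

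*Combined protocol and SAP*

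**What the plan says.** The section Data Management and Primary Statistical Analyses specifies mixed-effects two-way ANOVA models at alpha 0.05 "To test the main effects of time, treatment, and their interaction on the primary outcomes", followed by Fisher's LSD "to examine within and between group mean differences". Sex is tested in every model. The section then adds: "Other covariates that may be included in the models include race, change in body weight, and baseline SPPB scores".

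It does not define weight change (which visits, absolute or percent), and does not say which outcomes it applies to, when it would be included, whether it enters as a main effect or with time, or whether the unadjusted model stays primary. No other section fills these gaps.

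Related statements elsewhere:
- **Timing.** Under Exercise Interventions, subjects are randomised after V2 and weighed weekly during training. They are weighed again at V3, V4 and V5.
- **Outcomes.** Study Endpoints makes DXA muscle mass (Aim 1) and DXA body composition (Aim 2) primary, expressed as within- and between-group changes.
- **Hypothesis.** The trial is built to show that "the addition of LPA breaks in ST will enhance RE-induced improvements in muscle and cardiometabolic health in sedentary older adults", which is the REALPA-versus-RE contrast.
- **Use of results.** Sample Size, Power Analysis and Randomization says the data will be used to "estimate effect sizes for the primary and secondary outcomes, which we will use to inform our power analyses for a follow-up R01 application".

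**The concern.** Two of the three listed covariates are fixed before randomisation; weight change is not. REALPA and RE+AE are each planned to add about 500 kcal/wk of expenditure to the RE programme, so weight change is plausibly a consequence of assignment. Conditioning on it then no longer estimates the total effect of being assigned to the LPA breaks.

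For the DXA outcomes the problem is sharper than ordinary mediator adjustment. Fat, lean and bone make up body weight, so weight change is close to the sum of the outcomes being modelled. Holding the sum fixed makes any arm difference in fat appear as an opposite difference in lean. For fasting glucose, lipids and glucose tolerance, the issue is conditioning on a possible mediator, and its size has not been quantified.

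At stake are the central contrast of the trial and the effect sizes intended for the R01 power analysis. Because entry is optional and undefined, the choice of model could also be made after the results are seen.

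**Working it through.** **1. The plan's own figures.** No figure in the plan bears directly on the covariate. The recruitment arithmetic reproduces: 12/(1 - 0.20) = 15 per group and 36/(1 - 0.20) = 45 in total. Simulations below use 12 per arm.

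**2. A plausible effect on weight.** The planned REALPA-versus-RE energy contrast is 500 x 16 = 8,000 kcal. At an assumed 6,000 to 9,000 kcal per kg this is 8,000/9,000 = 0.9 kg to 8,000/6,000 = 1.3 kg, with full adherence and no compensation. A fat effect of -1.0 kg is therefore treated as near an upper bound.

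**3. Change-score or time-interacted entry.** Assume a true REALPA-minus-RE effect of -1.0 kg fat and 0 kg lean, independent fat and lean changes with SDs sF and sL, and weight change = fat change + lean change (bone negligible). Within arm, the slope of fat change on weight change is b = sF²/(sF² + sL²), and that of lean change is 1 - b. The arm effect on weight is -1.0 kg, so adjusted fat = -1 + b and adjusted lean = 1 - b. The two always sum to zero.

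| sF : sL | b | adjusted fat (kg) | adjusted lean (kg) |
|---|---|---|---|
| 1.0 : 1.5 | 1/3.25 = 0.308 | -0.69 | +0.69 |
| 1 : 1 | 1/2 = 0.500 | -0.50 | +0.50 |
| 1.5 : 1.0 | 2.25/3.25 = 0.692 | -0.31 | +0.31 |
| 2 : 1 | 4/5 = 0.800 | -0.20 | +0.20 |

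Simulation with three arms of 12 (sF 1.5, sL 1.0; 3,000 runs) gave -0.310 and +0.310. Results scale linearly: a true -0.5 kg at 1.5:1.0 becomes -0.15 fat and +0.15 lean.

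**4. Relaxing the identity** (sF 1.5, sL 1.0).
- With 0.7 kg disagreement between scale and DXA, the denominator is 3.25 + 0.49 = 3.74. Fat is -1 + 2.25/3.74 = -0.40 and lean is 1/3.74 = +0.27.
- For a regional lean measure carrying one-third of lean change, the spurious gain is (1/3)/3.25 = 0.10 kg; simulation with 0.3 kg added noise gave +0.106.

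**5. Error rates.** In a two-arm simulation (12 per arm, two-sided 0.05, same SDs, true -1.0 fat and 0 lean), power for fat falls from about 36% to 12%. The false-positive rate for lean rises from about 5% to 12%, or to about 20% if fat and lean changes correlate 0.3.

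**6. Main-effect entry, complete data.** In a random-intercept model with arm, time, arm-by-time and weight change, fitted to 60 simulated data sets, the interaction matched the unadjusted model to 6e-15. In one illustrative three-arm data set, the REALPA interaction for fat was -1.41 kg unadjusted, -1.41 with a main effect only, and -0.22 with weight change by time.

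The treatment main effect (mean of pre and post) does move. With an assumed baseline fat SD of 6 kg and correlation rho between baseline fat and fat change, the slope is (rho x 6 x 1.5 + 1.125)/3.25.
- rho = 0: slope 0.346, so -0.50 becomes -0.154. Applying that slope at each visit gives an artificial baseline difference of +0.35 kg and a post-training difference of -1.0 + 0.346 = -0.65 kg.
- rho = -0.3: -0.985.
- rho = +0.3: +0.677.

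**7. When there is no bias.** If two arms have the same mean weight change, their contrast is not biased. The simulated REALPA-versus-RE+AE contrast under equal weight change was +0.005 kg for fat and -0.005 kg for lean. A true -0.5 kg fat with +0.5 kg lean (no net weight effect) is also recovered without bias.

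**The case against.** The strongest reply is that the stated model is a pre/post ANOVA, in which an added covariate is most naturally a main effect. The primary endpoints are changes, the between-group comparison of changes is the treatment-by-time term, and that term is untouched with complete data. This is correct, and the 31% to 80% attenuation does not apply on that reading. But the plan does not specify that reading, and endpoints worded as changes invite a change-score analysis.

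The main-effect shift is also small against its sampling error. With the inputs in step 6 and rho = 0, the standard error is sqrt(36 + 2.25/4) x sqrt(2/12) = about 2.5 kg, so moving from -0.50 to -0.15 kg is about 0.14 SE; at rho of -0.3 and +0.3 the shifts are about 0.2 and 0.46 SE. That stands, and the main-effect range should carry little weight. The change-score shift is different: 0.69 kg against 1.5 x sqrt(2/12) = 0.61 kg.

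Other limits also stand. Entry is optional, every magnitude is assumed, and the -1.0 kg effect is large for unsupervised breaks. The plan does not say that adjusted estimates will feed the R01. The absence of bias for REALPA versus RE+AE is conditional on equal weight change. Taking rest as 1 MET, the prescriptions give 300 min x 1 MET = 5 MET-h/wk for LPA and 150 min x 3 METs = 7.5 MET-h/wk for AE, although both are described as about 500 kcal/wk, so that contrast is not cleared.

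None of this supplies a reason to keep an undefined post-randomisation covariate in the primary models.

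**Conclusion.** The concern holds. The plan permits a post-randomisation variable that is nearly the sum of two primary outcomes to enter the primary models, without a definition, a form of entry or an inclusion rule.

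If it enters a change-score or time-interacted model and REALPA changes weight relative to RE, the adjusted effects on whole-body fat and lean are pushed towards equal and opposite values and no longer estimate the total effect of assignment. The mirror image is only approximate when scale and DXA disagree or lean is regional. If weight change enters as a main effect only, with complete data, the change contrast is safe; the treatment main effect and group means shift, by little relative to their standard error.

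Confidence in the size is moderate, because it depends on assumed SDs, effects and correlations. The finding that the covariate is post-randomisation and unregulated does not depend on those assumptions. This should be corrected, though it does not undermine the design.

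**What to change.** Delete change in body weight from the covariate list for the primary and secondary models. Restrict covariates to baseline variables fixed in advance: sex, race, baseline SPPB and, if adjustment for body size is wanted, baseline body weight, which is already measured. Any model adjusted for weight change should be reported only as a labelled exploratory or mediation analysis, stating how weight change is defined and how it enters, and its effect sizes should not be used for the R01 power analysis.

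The cost is one sentence in the analysis section. No new data are needed, and the investigators can still explore weight change as a mechanism.
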